All biomarker measures will be summarized with descriptive statistics, i.e., percentages for categorical outcomes and means/medians for continuous outcomes, with corresponding standard errors and 95% confidence intervals. Responses will be tabulated by determined response and toxicities will be tabulated by type and grade. For IHC, the percentage of positive cells per area will be multiplied by the staining intensity for each tumor to determine quantitative expression pre- and post-treatment; a 25% change in expression will be considered a positive response. Patient level exploratory endpoints will be summarized using frequency (in %) if they are dichotomous or categorical and mean (std) if they are numerical respectively. Endpoints will be assessed of relations or associations using regression models, ANOVA models and logistical models respectively to accommodate numerical and categorical types of dependent and independent variables (i.e. endpoints).

Accrual Rate:

At the University of Cincinnati, we see approximately 300-350 new cases of HNSCC per year. Of those, approximately 100-150 stage III/IV HNSCC are treated with radiation +/- chemotherapy. Our institution conducted a retrospective analysis and identified twenty-eight patients over a 1-year period that were initially treated with definitive concurrent CRT or RT alone who subsequently developed local recurrence and required salvage resection. Based on this, we expect to accrue approximately 1-2 patients per month at UC. From the similar consideration to UC, we expect that the accrual rates would be 2 patients per month at Karmanos Cancer Institute. That will yield a combined 2-institution effective accrual rate of 3-4 patients per month. Thus we expect enrollment for this phase II study to be completed within 10-13 months based on 39 patients.

TABLE OF CONTENTS

STUDY SYNOPSIS	1
SECONDARY OBJECTIVES AND HYPOTHESES:	1
EXPLORATORY OBJECTIVES:	1
1.0 BACKGROUND & RATIONALE.....	1
1.1 PRODUCT DEVELOPMENT BACKGROUND	1
1.1.1 MECHANISM OF ACTION AND RATIONALE FOR USE OF DRUG	1
1.2 ADJUVANT TREATMENT IN HEAD AND NECK CANCER.....	2
2.0 RATIONALE.....	3
2.1 RATIONALE FOR THE TRIAL AND SELECTED SUBJECT POPULATION	3
2.2 EFFICACY ENDPOINTS.....	3
2.3 SAFETY ENDPOINTS	3
2.4 BIOMARKER RESEARCH/ENDPOINTS RATIONALE	4
3.0 ETHICAL CONSIDERATIONS	4
3.1 GOOD CLINICAL PRACTICE	4
3.2 INSTITUTIONAL REVIEW BOARD.....	4
3.3 INFORMED CONSENT	4
4.0 METHODOLOGY/INVESTIGATIONAL PLAN	5

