6.0 STUDY FLOW CHART

Trial Period	Screening	Treatment							Post-Treatment/Follow-up ^q
		1	2	3	4	5	6		
Scheduling Window (Days)	-28 to -1	0 ^(j)	± 3	± 3	± 3	± 3	± 3	30 Days post-discon +/- 3 ^(l)	Every 12 weeks +/- 4 weeks
Adjuvant Treatment (Week)		1	5	9	13	17	21		
Informed Consent	X								
Inclusion/ Exclusion Criteria ^(R)	X								
Demographics and Medical History ^(m)	X								
Prior and Concomitant Medication Review	X	X	X	X	X	X	X	X	
Nivolumab Administration ^(a)		X	X	X	X	X	X		
Post-study anticancer therapy status								X	
Survival and Disease Status ^(k)									X
Review Adverse Events		X	X	X	X	X	X	X ⁽ⁱ⁾	
Full Physical Examination	X							X	
Directed Physical Examination		X	X	X	X	X	X		X ^(c)
Vital Signs and Weight	X ⁽ⁿ⁾	X	X	X	X	X	X	X	

Trial Period	Screening	Treatment							Post-Treatment/Follow-up ^q
		1	2	3	4	5	6		
Scheduling Window (Days)	-28 to -1	0 ^(j)	± 3	± 3	± 3	± 3	± 3	30 Days post-discon +/- 3 ^(l)	Every 12 weeks +/- 4 weeks
Adjuvant Treatment (Week)		1	5	9	13	17	21		
ECOG Performance Status ^(b)	X		X	X	X	X	X		
Pregnancy Test – Urine or Serum -HCG	X ^(p)								
CBC with Differential	X ^(o)	X ^(o)	X	X	X	X	X	X	
Comprehensive Serum Chemistry Panel ^(d)	X ^(o)	X ^(o)	X	X	X	X	X	X	
Urinalysis	X ^(o)	X ^(o)			X			X	
T3, FT4 and TSH	X ^(o)	X ^(o)			X			X	X ^(h)
PT/INR, PTT	X ^(o)								
Tumor Imaging ^(e)	X								X ^(e)
Archival Tissue Collection ^(f)	X							X ^(f)	
Correlative Studies Blood Collection ^(g)		X	X					X ^(g)	

a) Nivolumab will start 28-77 days after surgery. Start of cycle on Day 1 +/- 3 days.

b) ECOG to be done prior to treatment administration. For Day 1, must be done within 10 days but does not need to be repeated for Day 1 only.

c) Only required if assessing for disease recurrence.

- d) Magnesium, Phosphorous, LDH, uric acid should also be checked as part of CMP labs.
- e) PET/CT and CT neck with contrast preferred for screening. CT neck with contrast and CT chest or MRI neck and chest is also acceptable. Neck imaging must be completed pre-operatively but chest imaging may be pre or post-operatively. Follow-up tumor imaging will be at discretion of treating physician but is not required per protocol.
- f) Archival Resected tissue will be collected from pathology and sectioned per procedure manual. If biopsy or resection is performed per SOC at recurrence, tissue will also be collected at that time for analysis.

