7.6 TUMOR TISSUE COLLECTION AND CORRELATIVE STUDIES BLOOD SAMPLING

Any subjects with oropharyngeal cancers must have documented HPV status (either by p16 or in situ hybridization).

Resected tissue, preferably a tissue block (at least 20, but prefer 30, FFPE slides and a tissue scroll if block not feasible) must be submitted and delivered to UCCI for analyses. If patient develops recurrence and undergoes standard of care biopsy or resection, the tissue will also be collected for analysis similar to above. Please see laboratory procedures manual for full details.

Blood samples will be collected at screening after resection and after first adjuvant dose of Nivolumab at week 5. A third collection will be collected at the 30 day post-discontinuation visit.

Detailed processing, shipping and handling will be provided in the laboratory procedures manual.

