7.6.3 PHARMACODYNAMIC EVALUATIONS

Please refer to the Laboratory Manual for PBMC Procedures.

Hematology	Chemistry	Urinalysis	Other
Hematocrit	Albumin	Blood	Serum β -human chorionic gonadotropin†
Hemoglobin	Alkaline phosphatase	Glucose	(β -hCG)†
Platelet count	Alanine aminotransferase (ALT)	Protein	Total triiodothyronine (T3)
WBC (total and differential)	Aspartate aminotransferase (AST)	Specific gravity	Free tyroxine (T4)
Red Blood Cell Count	Lactate dehydrogenase (LDH)	Microscopic exam (If abnormal)	Thyroid stimulating hormone (TSH)
Absolute Neutrophil Count	(CO_2 or biocarbonate)	Urine pregnancy test †	Prothrombin time PT/INR
Absolute Lymphocyte Count	Uric Acid		Partial Thromboplastin Time (PTT)
	Calcium		
	Chloride		Blood for correlative studies
	Glucose		
	Phosphorus		
	Potassium		
	Sodium		
	Creatinine		
	Magnesium		
	Total Bilirubin		
	Direct Bilirubin (If total bilirubin is elevated above the upper limit of normal)		
	Total protein		
	Blood Urea Nitrogen		
	Blood Urea Nitrogen		
† Done on all women of child-bearing potential			

Immunohistochemistry/Immunofluorescence

Archived resected tissue and if available recurrent biopsy or surgical tissue will be sent to the University of Cincinnati pathology department for processing. FFPE sections will be used to analyze the immune cell phenotype (markers include CD4, CD8, T reg, PD-1, PD-L1, granzyme expression and KI-67).

RNA Sequencing for Inflammatory Gene Signature

FFPE tissue will also undergo RNA and/or whole exome sequencing to identify an inflammatory gene signature and possible genetic alterations in responders versus non-responders.

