9.6.3 BIOMARKER ASSESSMENTS

All biomarker measures will be summarized with descriptive statistics, i.e., percentages for categorical outcomes and means/medians for continuous outcomes, with corresponding standard errors and 95% confidence intervals. Responses will be tabulated by determined response and toxicities will be tabulated by type and grade. For IHC, the percentage of positive cells per area will be multiplied by the staining intensity for each tumor to determine quantitative expression in pre treatment tissue and post-treatment if available. ; We will use descriptive statistics and graphical displays to evaluate change in plasma markers and flow cytometry markers between pre- and post-treatment.

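### The synopsis labels a 25% pre-to-post change in tumour IHC a positive response, but post-treatment tumour is collected only at recurrence, and Section 9.6.3 omits the rule

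*Combined protocol and SAP*

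**What the plan says.** The Biomarker Assessments paragraph of the synopsis defines the IHC score as the percentage of positive cells per area "multiplied by the staining intensity for each tumor to determine quantitative expression pre- and post-treatment". It then adds that "a 25% change in expression will be considered a positive response". No marker is named and no direction is given.

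Section 9.6.3 builds the same score "to determine quantitative expression in pre treatment tissue and post-treatment if available". It has no 25% rule. Both paragraphs also contain a general sentence saying that responses will be tabulated.

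Three places govern tumour tissue after treatment:

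- Section 6.0, footnote f: "If biopsy or resection is performed per SOC at recurrence, tissue will also be collected at that time for analysis".
- Section 7.6: "If patient develops recurrence and undergoes standard of care biopsy or resection, the tissue will also be collected for analysis".
- Section 7.6.3, on what goes to IHC: "Archived resected tissue and if available recurrent biopsy or surgical tissue will be sent".

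**The concern.** A response category should be assessable in patients who do well and in those who do badly. Here the second specimen exists only because the tumour came back, and recurrence is a failure on the primary endpoint, DFS. The classification is therefore confined to patients with a DFS event.

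The missing direction adds to the problem. The panel in Section 7.6.3 includes CD4, CD8, Treg, PD-1, PD-L1, granzyme and Ki-67. A 25% fall in CD8 and a 25% rise in CD8 would both be positive, as would a 25% rise in Treg.

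The vocabulary also clashes. Sections 2.4 and 7.6.3 speak of responders and non-responders, and Section 2.4 frames the gene-signature comparison as patients who did not relapse against those who did. On that usage, every IHC positive response would belong to a clinical non-responder. A table produced under the synopsis rule could not be interpreted.

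**Working it through.** No sample size, power or error rate rests on the 25% rule, so there is no figure in the plan to reproduce. The check traces where tissue can come from and then puts a ceiling on the number of pairs.

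**Step 1. Can post-treatment tumour exist without recurrence?**

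- Table 2 (Section 5.6) starts nivolumab 4-11 weeks after surgery. Footnotes a and j of Section 6.0 say 28-77 days, which is the same window (4 × 7 = 28; 11 × 7 = 77). The resection specimen is therefore pre-treatment. The text under Table 2 mentions a pre-surgical dose that neither the table nor the flow chart contains. I work from the table and chart; the passages need reconciling.
- Section 4.3, criterion 2, excludes gross measurable residual disease, so there is normally no tumour to re-sample in a patient who has not relapsed.
- The flow chart marks tissue collection in the 30-day post-discontinuation column, but that mark carries footnote f, so it depends on recurrence. No on-treatment or end-of-treatment biopsy is scheduled.

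A pre/post IHC pair therefore requires a recurrence and a standard-of-care procedure.

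**Step 2. How many patients could be scored?**

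Inputs: N = 39 enrolled; 2-year DFS of 33% (null) and 53% (alternative), all from the synopsis sample-size paragraph. Assume no dropout, and that every DFS event by 2 years is a recurrence with tissue.

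Ceiling = N × (1 − 2-year DFS)

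- DFS 33%: 39 × 0.67 = 26.1
- DFS 53%: 39 × 0.47 = 18.3

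With the 35 patients that the synopsis gives before the dropout allowance, the figures are 35 × 0.67 = 23.5 and 35 × 0.47 = 16.5.

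**Step 3. Why the real number is lower.**

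DFS events include deaths without recurrence, which give no tissue. Section 7.5.8 only recommends biopsy at relapse and accepts follow-up imaging instead. The documents give no tissue yield, so I assume that 50% to 75% of events provide a pair:

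| 2-year DFS | Ceiling (39 patients) | 75% yield | 50% yield |
|---|---|---|---|
| 33% | 26.1 | 19.6 | 13.1 |
| 53% | 18.3 | 13.7 | 9.2 |

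**Step 4. Who cannot be scored?**

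Patients disease-free at 2 years number 39 × 0.33 = 12.9 or 39 × 0.53 = 20.7. They contribute no pair unless they relapse later within follow-up, and then they too are relapsed patients.

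**Step 5. Do the two texts agree?**

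They do not. Section 9.6.3 gives the same score without the 25% rule and makes post-treatment tissue conditional on availability. That condition does not remove the selection, because tissue is available only after a recurrence and a procedure.

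**The case against.** The strongest reply is that the statistical section has already dropped the rule. Section 9.6.3 is descriptive and concedes that post-treatment tissue may be missing, so what remains may be one left-over clause in the synopsis. That is plausible and limits the weight of the point. But the clause stands in the current version, and the documents do not say which text prevails.

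A reader might infer that the exploratory comparison of relapsed with non-relapsed patients is defeated. The documents do not support that. Exploratory objective 1 asks for an immunophenotype before PD-1 inhibition, and Section 2.4 specifies lymphocytes present before drug. The exploratory endpoint in the synopsis attaches before-and-after change to peripheral blood, which Section 7.6 schedules without any condition of relapse. None of this needs post-treatment tumour.

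A reader might also infer that the trial would present an IHC response rate as evidence of drug effect. No passage uses the score that way; efficacy is DFS.

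Finally, the event counts could be mistaken for expected numbers of pairs. They are not, for the reasons in Step 3. Nor are patients disease-free at 2 years permanently without tissue: Section 7.7.4 follows patients for up to 2 years after moving into follow-up at the last dose, so a later relapse could supply a specimen.

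**Conclusion.** The point holds as a minor error in an exploratory analysis. The synopsis sets a response rule that can be applied only to relapsed patients with tissue, counts change in either direction as positive, and conflicts with Section 9.6.3.

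The expected number who could be scored from events by 2 years is at most about 18 to 26 of 39, at DFS of 53% and 33% respectively, and fewer in practice. These are expected values under the plan's own DFS figures, with no dropout and with tissue from every event. The 50% to 75% yield range is my assumption.

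The restriction to relapsed patients does not depend on those numbers; it follows from the collection rules. No primary or secondary analysis, sample size or error rate changes, and the pre-treatment immunophenotype aim is intact.

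**What to change.** 1. Delete the 25% positive-response clause from the synopsis and align the paragraph with Section 9.6.3.
2. In both places, use wording such as: *Paired tumour IHC will be summarised descriptively as the change from pre-treatment tissue to tissue obtained at recurrence, in relapsed patients with both specimens. No response category or rate will be derived.*
3. In both places, remove the sentence on tabulating responses as far as it applies to IHC. The part on tabulating toxicities can stay.
4. State that the relapsed versus not-relapsed comparison uses pre-treatment tissue, as exploratory objective 1 and Section 2.4 already intend. Say archived biopsy or resection rather than resection alone, because inclusion criterion 6 in Section 4.2 accepts either.

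The cost is wording in two paragraphs. No samples, assays or visits are added. The sponsor gives up only an IHC response rate that could not have been interpreted.

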1.0 BACKGROUND & RATIONALE

1.1 PRODUCT DEVELOPMENT BACKGROUND

1.1.1 MECHANISM OF ACTION AND RATIONALE FOR USE OF DRUG

Immunotherapeutic approaches for cancer treatment have existed for several decades. Recent advances in immunotherapeutics have recognized key regulatory pathways that are involved in the anti-tumor response. Multiple immune checkpoint molecules are up regulated during the immune response in an attempt to prevent autoimmune damage to normal tissue by maintenance of tolerance to self-antigens. Cytotoxic T-lymphocyte antigen-4 (CTLA-4) as well as programmed death-1 (PD-1) and its ligands are key inhibitors of the anti-tumor response. CTLA-4 acts a dampener in lymph nodes preventing early activation of T cells whereas PD-1 is induced on T cells after activation by immune stimulation either by infection or tumor progression. Interestingly, the negative immune cell regulator, PD1 ligand-1 (PD-L1), has been found to be up regulated on many tumors including HNSCC.

The importance of intact immune surveillance in controlling outgrowth of neoplastic transformation has been known for decades. Accumulating evidence shows a correlation between tumor-infiltrating lymphocytes (TILs) in cancer tissue and favorable prognosis in various malignancies. In particular, the presence of CD8+ T-cells and the ratio of CD8+ effector T-cells / FoxP3+ regulatory T-cells seems to correlate with improved prognosis and long-term survival in many solid tumors.

PD-1 (or CD279), a 55-kilodalton Type 1 transmembrane protein is a member of the CD28 family of T-cell co-stimulatory receptors that include immunoglobulin super family members CD28, CTLA-4, ICOS, and BTLA. PD-1 is highly expressed on activated T cells and B cells. PD-1 expression can also be detected on memory T-cell subsets with variable levels of expression. Two ligands specific for PD-1 have been identified: PD-L1 (also known as B7-H1 or CD274) and PD-L2 (also known as B7-DC or CD273). PD-L1 and PD-L2 have been shown to down-regulate T-cell activation upon binding to PD-1 in both murine and human systems. The interaction of PD-1 with its ligands, PD-L1 and PD-L2, which are expressed on antigen-presenting cells (APCs) and DCs, transmits negative regulatory stimuli to down-modulate the activated T-cell immune response. The absence or inhibition of PD-1 in murine models has resulted in the development of various autoimmune phenotypes and autoimmune diseases. Taken together, these results suggest that inhibition of PD-1 binding to its ligands has the potential to activate T-cell responses. Since these responses are variable and dependent upon various host genetic factors, PD-1 deficiency or inhibition is not accompanied by a universal loss of tolerance to self-antigens.

Tumors can express tumor-specific antigens as a result of mutational burden, and ongoing immune surveillance is believed to control the development of many tumors. Tumor progression may depend on the acquisition of mechanisms that permit them to evade an effective immune response.

One such mechanism of evasion may be the expression of ligands, which engage inhibitory receptor(s) on anti-tumor T-cells of many tumors. PD-L1 expression has been found on a number of tumors and may be a mechanism by which tumors can directly engage PD-1 to evade an effective anti-tumor immune response. Expression of IFN- γ by activated T cells is known to induce PD-L1 expression in tumors. PD-1 engagement on T-cells by PD-L1-positive APC or PD-L1-positive tumor cells in the tumor microenvironment may limit effective immune responses. Conversely, PD-L1 expression may be a positive prognostic factor as it may indicate infiltration of tumor-specific T cells that secrete IFN-gamma, which up regulates PD-L1 expression. Consistent with this hypothesis is the co-localization of lymphoid cell infiltrates and PD-L1 staining observed in human melanoma lesions.

Nivolumab (anti-PD-1 mAb) is a fully human monoclonal immunoglobulin (Ig) G4 antibody that binds to the programmed death-1 (PD-1) cell surface membrane receptor; a negative regulatory molecule expressed by activated T and B-lymphocytes. It has been approved in the metastatic setting for lung cancer, renal cell cancer, melanoma, and most recently in metastatic HNSCC. This is based on the Checkmate-141 phase III clinical trial, in which 361 patients with platinum-refractory, recurrent or metastatic squamous cell carcinoma of the head and neck were randomly assigned to either Nivolumab (3 mg/kg every two weeks) or a single-agent investigator's choice of therapy (methotrexate, docetaxel, or cetuximab).¹ Overall survival (OS) was significantly improved in Nivolumab arm (7.5 vs. 5.1 months) and it was noted that OS increased with immunotherapy in patients with programmed death ligand 1 (PD-L1) expression $\geq 1\%$.¹ Several studies are now ongoing to study PD-1 inhibitors in the upfront and adjuvant setting. However, no study yet exists to study the inhibitor in HNSCC patients who have undergone salvage resection.

1.2 ADJUVANT TREATMENT IN HEAD AND NECK CANCER

Head and neck squamous cell cancer (HNSCC) is the sixth most common cancer type worldwide and accounts for approximately 350,000 deaths per year.^{2,3} Approximately 30 to 40% of patients with HNSCC present with stage I or II (early stage) disease.⁴ In general, these patients are treated with either primary surgery or definitive radiation therapy (RT).⁴ However, patients who present with advanced stage disease (Stage III or IV) not only pose a treatment challenge but also have a higher risk of both local recurrence and distant metastasis. Combined modality approaches (surgery, RT, and/or chemotherapy) are generally required to optimize the chance for long-term disease control for patients with advanced stage disease. These combined modality approaches include primary surgery followed by postoperative RT or concurrent chemoradiotherapy (CRT), induction chemotherapy (the addition of chemotherapy prior to surgery and/or RT), concurrent CRT without surgery, or sequential therapy (induction chemotherapy followed by concurrent CRT) without surgery.

Despite advances in the treatment of localized HNSCC, 15 to 50% of patients will develop recurrent disease⁵, which is further, complicated by lack of reliable salvage treatment options. Tissues of the head and neck such as skin, nerves, blood vessels, and spinal cord normally receive maximally tolerated radiation doses during the initial course of radiation therapy (RT), therefore, re-irradiation exposes these tissues to more toxicities and complications. This often leaves surgical salvage as the only potential curative intent treatment for recurrent head and neck cancer which confers local control rates of 33-50% and a long term overall survival of 20-40% suggesting that novel treatments are necessary in order to improve outcomes in these high risk patients.^{6,7}

In the primary adjuvant setting, two pivotal studies published in 2004 (Bernier et al., and Cooper et al.) demonstrated increased progression free and overall survival (Bernier et al) in patients with high-risk features who received adjuvant concurrent cisplatin and radiation albeit with higher toxicity over radiation alone.^{8,9} However, in the salvage setting, there is no standard of care for patients who have high risk (extra capsular extension of lymph nodes and/or positive margins) or intermediate risk (perineural invasion, lymphovascular invasion, close margins and multiple lymph node involvement) features after resection. In addition patients have often already received maximum radiation dose and chemotherapy alone has not shown any benefit in these patients. Therefore, there is currently little evidence to recommend further adjuvant therapy even in setting of high or intermediate pathological features despite the fact that these patients are at high risk of metastasis.⁷

